#### 4.1.2 Secondary Parameters

The secondary effectiveness endpoints are:

- The percentage of patients with virological response (HCV RNA  $< 50$  IU/mL) at EoT (defined as last intake of ABBVIE REGIMEN or ribavirin)
- The percentage of patients with relapse (defined as HCV RNA  $< 50$  IU/mL at EoT followed by HCV RNA  $\geq 50$  IU/mL)
- The percentage of patients with breakthrough (defined as at least one documented HCV RNA  $< 50$  IU/mL followed by HCV RNA  $\geq 50$  IU/mL during treatment).
- Rapid virological response at week 4 (RVR 4, i.e. patients with HCV RNA  $< 50$  IU/mL at week 4)
- Sustained virological response 24 weeks after EoT (SVR24, i.e. patients with HCV RNA  $< 50$  IU/mL 24 weeks after EoT)
- Sustained virological response 48 weeks after EoT (SVR48, i.e. patients with HCV RNA  $< 50$  IU/mL 48 weeks after EoT)
- The number and percentage of patients meeting each and any of the following SVR12 non-response categories:
  - On-treatment virologic failure (breakthrough [defined as above] or failure to suppress [each measured on-treatment HCV RNA value  $\geq 50$  IU/mL])
  - Relapse (defined as HCV RNA  $< 50$  IU/mL at EoT followed by HCV RNA  $\geq 50$  IU/mL post-treatment for subjects who complete treatment [not more than 7 days shortened])
  - Premature study drug discontinuation with no on-treatment virologic failure

- Missing SVR12 data and/or none of the above criteria

Further secondary variables are:

- Type of treatment regimen ( $\pm$  Dasabuvir,  $\pm$  RBV, intended and actual combination, dose and duration)
- Adherence
  - Percentage of the DAA dose taken in relation to the target dose of DAA (cumulative dose taken divided by target dose in percent)
  - Percentage of the RBV dose taken in relation to the target dose of RBV (cumulative dose taken divided by target dose in percent)
  - Percentage of missed RBV treatment days in relation to the target number of RBV treatment days
- Co-morbidities and concomitant medication
- Serious and non-serious adverse events and pregnancy occurrences
- Questionnaires on PROs: e.g. PAM-13, FACIT-Fatigue, PRISM and work productivity and activity impairment (WPAI) questionnaire prior to treatment initiation, at EoT as well as 12, 24 and 48 weeks after EoT

No data will be imputed for any effectiveness or safety analyses except for the analyses of the HCV RNA endpoints and PRO questionnaires (if applicable). For further details see sections 4.2.3 and 4.2.7.2.3, respectively.

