## 9.7 Data Analysis

### 9.7.1 Analysis Population, Time Windows and Handling of Missing Data

The target population (TP) is defined as all patients who fulfill the criteria specified in Section 9.2.1. The core population (CP) is defined as all patients of the TP, who have started the treatment combination recommended in the current local label for their disease characteristics. Patients not receiving the treatment recommended in the local label will be summarized in the non-core population (NCP). In addition, the core population with sufficient follow-up data (CPSFU) is defined as all CP patients, who fulfil one of the following criteria:

- (1) evaluable HCV RNA data  $\geq 70$  days after the last actual dose of the ABBVIE REGIMEN (i.e. data within the SVR12 time window)
- (2) a HCV RNA value  $\geq 50$  IU/mL at the last measurement post-baseline (i.e. no virological response achieved at the last measurement on-treatment or post-treatment)
- (3) HCV RNA  $< 50$  IU/mL at the last measurement post-baseline, but no HCV RNA measurement  $\geq 70$  days after the last actual dose of the ABBVIE REGIMEN due to reasons related to safety (e.g. dropped out due to AE) or incomplete efficacy information (e.g. virologic failure such as relapse is reported in the eCRF but date and value of the corresponding HCV RNA test is missing). This means only patients who had virological response at their last on-treatment or post-treatment measurement, but had no HCV RNA measurements  $\geq 70$  days post-treatment for reasons not related to safety or effectiveness (e.g. lost-to-follow-up or patient not willing to perform an additional HCV RNA test  $\geq 70$  days post-treatment) will be excluded from this analysis.

The Safety Population (SP) is defined as all patients who received at least one dose of the ABBVIE REGIMEN.

In accordance with the non-interventional nature of the study all HCV RNA measurements will be performed at the sole discretion of the physician and all HCV RNA measurements have to be entered into the eCRF. All recorded HCV RNA values will be assigned to appropriate time points (baseline, on-treatment visits, EoT visit, post-treatment visits). The time windows for the assignments will be specified in the statistical analysis plan (SAP).

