**Core Population with Sufficient Follow-up [CPSFU {12, 24, 48}]**

In addition, the core population with sufficient follow-up data regarding SVR12, SVR24 or SVR48, respectively, is defined as all CP patients,

- who have evaluable HCV RNA data  $\geq 70$  days,  $>126$  days or  $>210$  days, respectively, after the last actual dose of the ABBVIE REGIMEN
- or a HCV RNA value  $\geq 50$  IU/mL at the last measurement post-baseline
- or had HCV RNA  $<50$  IU/mL at the last measurement post-baseline, but no HCV RNA measurement  $\geq 70$  days,  $>126$  days or  $>210$  days, respectively, after the last actual dose of the ABBVIE REGIMEN due to reasons related to safety (e.g. dropped out due to adverse event) or virologic failure (e.g. virologic failure such as relapse is reported in the electronic case report form (eCRF) but date and value of the corresponding HCV RNA test is missing).

This means only (1) patients who had virological response at their last on-treatment or post-treatment measurement, but had no post-treatment HCV RNA measurements  $\geq 70$  days,  $>126$  days or  $>210$  days, respectively, for reasons not related to safety or effectiveness (e.g. lost-to-follow-up or patient not willing to perform an additional HCV RNA test  $\geq 70$  days,  $>126$  days or  $>210$  days post-treatment, respectively) and (2) patients who had no post-baseline HCV RNA measurements for reasons not related to safety or effectiveness, and (3) patients with missing end of treatment date for reasons not related to safety or effectiveness, will be excluded from this analysis.

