**Table 3 - Analysis Time Windows for HCV RNA**

Phase	Time point	Time Window
Pre-Treatment	Baseline	Last value prior to start of study treatment (i.e. $\leq$ study day 1)
On-treatment		Study day during treatment period^# (Study day 1 = first treatment day)
Treatment Week	4 (RVR*)	15 - 42^
EoT	Actual EoT	Study day of last dose# (28 days prior to last dose - 7 days post last dose)
Post Treatment	12 weeks (SVR 12 window)	$\geq$ 70-126 days post last dose
	24 weeks (SVR24 window)	127-210 days post last dose
	48 weeks (SVR48 window)	> 210 days post last dose

^values must also be  $\leq$  7 days post last dose

#  $\geq$ study day 2

\*RVR = rapid virological response

All reported safety laboratory test results will be assigned to one of the time points using the time windows specified in the table below.

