#### 4.2.3 Handling of missing data

No data will be imputed for any effectiveness or safety analyses except for the analyses of the HCV RNA endpoints and certain PRO endpoints. The discussion of missing data imputation for the PRO endpoints is included in section 4.2.7.2.3.

HCV RNA values will be selected for an RVR, EOTR and SVR analysis based on visit windows as defined in Table 4. When there is no HCV RNA value in a visit window based on defined visit windows, the closest values before and after the window, regardless of the value chosen for the subsequent and preceding window, will be used for the flanking imputation described below. For analysis of RVR, EOT and SVR, if a subject has a missing HCV RNA value at a post-Day 1 visit but with undetectable or unquantifiable (LLoD or LLoQ  $\leq$ 50 IU/mL) HCV RNA levels at both the preceding value and succeeding value, the HCV RNA level will be considered undetectable or unquantifiable, respectively, at this visit for this subject. In addition, if a subject has an

unquantifiable HCV RNA level at the preceding value and an undetectable HCV RNA level at the succeeding value, or vice versa, the HCV RNA level will be imputed as unquantifiable at this visit for this subject.

For analyses of RVR, subjects still missing a value for the visit after flanking imputation will be considered as a failure. For EoTR and SVR analysis, if there is no value in the appropriate window after flanking imputation but there is an HCV RNA value after the window, then it will be imputed into the EoTR or SVR window respectively. Subsequent to this flanking and backward imputation, if the HCV RNA value remains missing at a specific time point, then the subject will be considered as virological failure at this time point (i.e., not undetectable or unquantifiable).

If a subject starts another treatment for HCV, then all HCV RNA values for this subject measured on or after the start date of the new HCV treatment will be excluded from analyses. The subject will be considered a failure for summaries of viral response at all time points after the start of the new HCV treatment.

Due to the non-interventional nature of this study several different methods for determination of the HCV RNA value can be applied. For the purpose of the statistical analysis, a HCV RNA measurement is considered <50 IU/mL,

- if a PCR test was used

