### **Non-Response**

In another table, the numbers and the percentages of the SVR12 non-responder categories and responder will be summarized for CP patients, overall and stratified by genotype and cirrhosis status. The following SVR12 non-response categories will be considered:

- On-treatment virologic failure (breakthrough [defined as at least one documented HCV RNA  $<50$  IU/mL followed by HCV RNA  $\geq 50$  IU/mL during treatment] or failure to suppress [each measured on-treatment HCV RNA value  $\geq 50$  IU/mL])
- Relapse (defined as HCV RNA  $<50$  IU/mL at EoT followed by HCV RNA  $\geq 50$  IU/mL post-treatment and completed treatment as defined previously)
- Death and none of the above
- Premature study drug discontinuation with no on-treatment virologic failure and none of the above
- Insufficient virological response, other than those mentioned above (patients for whom insufficient virological response was reported, or who had HCV RNA  $\geq 50$  IU/mL post EoT) and none of the above
- Missing SVR12 data and/or none of the above criteria

Virological response rates and non-response categories will be displayed for patients who completed treatment with ABBVIE regimen, as well.

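### Failure to suppress has no minimum time on treatment, so the SVR12 non-response breakdown labels some early stoppers, deaths and losses as on-treatment virologic failures

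*SAP*

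**What the plan says.** SAP 4.1.2 makes the breakdown of SVR12 non-response a secondary effectiveness endpoint. Its first category, on-treatment virologic failure, is met by breakthrough or by "failure to suppress [each measured on-treatment HCV RNA value" at or above 50 IU/mL. Protocol 9.7.3.2 has the same definition. Neither document sets a minimum time on treatment or a minimum number of samples.

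SAP Table 3 lets on-treatment HCV RNA values run from study day 2 to 7 days after the last dose. The end-of-treatment window is "28 days prior to last dose - 7 days post last dose", so an early stopper's only early value can also be the end-of-treatment value.

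SAP 4.2.7.2.1 (Non-Response) fixes the precedence. Below on-treatment virologic failure and relapse come "Death and none of the above", then "Premature study drug discontinuation with no on-treatment virologic failure and none of the above", then other insufficient response, then missing data. For SVR12 itself, SAP 4.2.3 says that "if the HCV RNA value remains missing at a specific time point, then the subject will be considered as virological failure at this time point".

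Three other provisions matter:
- SAP 4.1.2 limits the relapse category to patients who completed treatment (shortened by no more than 7 days). The protocol's relapse category has no such limit.
- SAP 4.2.7.2.1 repeats the breakdown in patients who completed the regimen.
- SAP 4.2.5 tabulates the main reason for early termination and separates adverse events from virological reasons.

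**The concern.** The breakdown should tell a reader whether non-response came from the virus not being controlled or from treatment or follow-up ending early. As written, the timing of one sample can decide this. An early value of at least 50 IU/mL does not make a patient a failure if a later on-treatment value is below 50, because then not every value is at or above 50. The same early value does make the patient a failure if treatment or follow-up ends before a second sample. The SAP also treats a value below 50 IU/mL in the day 15–42 window as a separate endpoint, which it calls rapid response. So under its own terms an early value at or above 50 does not establish that suppression failed.

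HCV RNA is sampled at the physician's discretion, so single early samples are plausible. The adverse-event stopper could also appear as an adverse-event termination in the SAP 4.2.5 table and as a virologic failure in the non-response table. The SAP keeps early stoppers out of relapse but has no matching condition for failure to suppress.

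**Working it through.** **1. The plan's own figure.** SAP 3.2 and Protocol 9.5 give n = 620, SVR12 = 95% and a two-sided 95% Wilson interval of 93.0–96.5, width 3.5%. With p = 0.95, n = 620, z = 1.96:

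- centre = (p + z²/2n)/(1 + z²/n) = 0.95310/1.00620 = 0.9472
- half-width = z·√(p(1−p)/n + z²/4n²)/(1 + z²/n) = 0.0173
- interval 92.99–96.46, width 3.47

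This matches the table. The documents give no figure for on-treatment virologic failure.

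**2. The rules applied to individual non-responders.**

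| Course | As written | With a minimum exposure |
|---|---|---|
| One early value ≥50, stops for an adverse event | On-treatment virologic failure | Premature discontinuation |
| One early value ≥50, dies | On-treatment virologic failure | Death |
| One early value ≥50, lost | On-treatment virologic failure | Premature discontinuation or missing |
| Early value ≥50, next value <50, stops for an adverse event | Premature discontinuation | Premature discontinuation |
| One early value ≥50, completes, no later on-treatment sample, no SVR12 data | On-treatment virologic failure | Missing |
| Early values all ≥50, stopped for virological non-response | On-treatment virologic failure | Depends on whether an exception is written |

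The first and fourth rows differ only in whether a second sample was taken. The last row shows that a bare time limit would hide a genuine failure.

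**3. Primary endpoint.** Every patient in the table is an SVR12 non-responder under either rule. Core-population SVR12 stays at 589/620 = 95.0% (93.0–96.5).

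**4. Size in the breakdown.** Expected non-responders are 620 × 0.05 = 31. Let k be the number affected and v the on-treatment failures that would remain under the rule. The documents give neither, so both are assumptions.

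- One patient: 1/620 = 0.16 points
- k = 3: 3/620 = 0.48 points; 3/31 = 10% of non-responders
- k = 6: 6/620 = 0.97 points; 6/31 = 19% of non-responders

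| v | Rate with rule | As written, k = 3 | As written, k = 6 |
|---|---|---|---|
| 3 | 3 (0.48%) | 6 (0.97%) | 9 (1.45%) |
| 6 | 6 (0.97%) | 9 (1.45%) | 12 (1.94%) |
| 10 | 10 (1.61%) | 13 (2.10%) | 16 (2.58%) |

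The reported count doubles only when k equals v.

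**5. Strata.** The table is split by genotype and cirrhosis. In the plan's 62-patient subgroup at 95%, expected non-responders are 62 × 0.05 = 3.1, so one patient is about a third of that stratum's breakdown.

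**The case against.** The strongest reply is that the plan already shows most of what is needed. The completer table removes known early stoppers, and SAP 4.2.5 gives reasons for termination, so a reader can compare outputs. This stands as mitigation. It does not correct the main core-population table, and the completer table still mislabels a completer with one early sample and no later data.

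A second reply is that a plain time limit would move a patient stopped early for virological non-response out of virologic failure and so flatter the regimen. This is right, and the fix needs an exception for it. It is also right that day 42 is only the edge of a visit window. The word rapid is not evidence of how fast suppression should occur, and the documents yield no cut-off of their own.

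A reader might also infer that the sensitivity population with sufficient follow-up (CPSFU) is biased downward. It keeps anyone with a value of at least 50 "IU/mL at the last measurement post-baseline", however early, but drops patients lost for unrelated reasons after a value below 50. If 3 to 6 such patients were dropped as well, SVR12 would rise from 589/620 = 95.0% to 589/617 = 95.5% or 589/614 = 95.9%. The documents do not support treating this as an error:
- Adverse-event stoppers stay in under the safety criterion whatever their last value.
- The SAP excludes "patients with missing end of treatment date for reasons not related to safety or effectiveness", which may already remove many patients lost on treatment. Its rank against the failure criterion is not stated.
- The criterion follows the protocol, which explains it as "no virological response achieved at the last measurement on-treatment or post-treatment".
- CPSFU12 results were displayed at interim analyses, and dropping observed values of at least 50 now could only raise the rate.

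**Conclusion.** The gap is real and confined to the non-response breakdown. An early sample at or above 50 IU/mL, with none later, is enough to label a non-responder who stops for an adverse event, dies or is lost as an on-treatment virologic failure. The error runs one way, towards virologic failure and away from the lower-ranked categories. The 10–19% figure rests on the planned 620 patients, 95% SVR12 and an assumed 3 to 6 affected patients. The true number could be zero.

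Two stronger readings should not be drawn. Primary SVR12 is not biased, since these patients are non-responders either way. Nor do the documents use this breakdown to support claims about potency; the objectives are descriptive or exploratory. This is a minor point, worth settling because it concerns a named secondary endpoint.

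**What to change.** In SAP 4.1.2 and 4.2.7.2.1, keep the requirement that every measured on-treatment value is at or above 50 IU/mL, and add that failure to suppress counts only if one of these holds:
- at least one such value falls after a prespecified minimum exposure, for example after study day 42, the end of the SAP's week-4 window; or
- the recorded reason for early termination is virological non-response, rebound or breakthrough, or resistance to the antivirals.

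Classify the remaining patients under death, premature discontinuation or missing data, in the existing order. Note the departure from Protocol 9.7.3.2, as SAP 4.1.1 already does for the SVR12 window. A footnote with the count under the protocol definition would keep the change transparent, since interim breakdowns have already been produced. Leave the CPSFU failure criterion unchanged.

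The cost is a sentence or two in the SAP and a small programming change, with no new data. A few patients change category. The cut-off is an analytic choice about classification, not a clinical rule. The sponsor may choose another, provided it is fixed before the final analysis.

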## 4.2 Statistical and Analytical Methods

### 4.2.1 Analysis Populations and Analysis Groups

#### Population of Patients Enrolled [EP]

The population of patients enrolled comprises all patients who voluntarily sign and date a patient authorization to use and/or disclose his/her anonymized health data prior to inclusion into the study and data were captured in the eCRF.

#### Target Population [TP]

Patients will be included if the following applies:

- Age at least 18 years
- Confirmed CHC with genotype 1 and/or 4 only, receiving combination therapy with the interferon-free ABBVIE REGIMEN  $\pm$  RBV. The prescribed ABBVIE REGIMEN needs to be known.
- Have voluntarily signed and dated a patient authorization to use and/or disclose his/her anonymized health data prior to inclusion into the study
- Must not be participating or intending to participate in a concurrent interventional therapeutic trial

**Core Population [CP]**

The core population is defined as all patients of the target population (TP) (definition see above), who are adequately treated according to the standard of care and within local label recommendations for their specific disease characteristics (cirrhotic status, genotype). The following patients will be excluded from the CP:

- Patients with unknown fibrosis status
- Cirrhotic patients with genotype 1a not receiving ribavirin
- Patients with genotype 1 for whom 2DAA instead of 3DAA is prescribed
- Patients with genotype 4 not receiving RBV

**Non-Core Population [NCP]**

Patients in the TP who are not in the CP.

**Core Population with Sufficient Follow-up [CPSFU {12, 24, 48}]**

In addition, the core population with sufficient follow-up data regarding SVR12, SVR24 or SVR48, respectively, is defined as all CP patients,

- who have evaluable HCV RNA data  $\geq 70$  days,  $>126$  days or  $>210$  days, respectively, after the last actual dose of the ABBVIE REGIMEN
- or a HCV RNA value  $\geq 50$  IU/mL at the last measurement post-baseline
- or had HCV RNA  $<50$  IU/mL at the last measurement post-baseline, but no HCV RNA measurement  $\geq 70$  days,  $>126$  days or  $>210$  days, respectively, after the last actual dose of the ABBVIE REGIMEN due to reasons related to safety (e.g. dropped out due to adverse event) or virologic failure (e.g. virologic failure such as relapse is reported in the electronic case report form (eCRF) but date and value of the corresponding HCV RNA test is missing).

This means only (1) patients who had virological response at their last on-treatment or post-treatment measurement, but had no post-treatment HCV RNA measurements  $\geq 70$  days,  $>126$  days or  $>210$  days, respectively, for reasons not related to safety or effectiveness (e.g. lost-to-follow-up or patient not willing to perform an additional HCV RNA test  $\geq 70$  days,  $>126$  days or  $>210$  days post-treatment, respectively) and (2) patients who had no post-baseline HCV RNA measurements for reasons not related to safety or effectiveness, and (3) patients with missing end of treatment date for reasons not related to safety or effectiveness, will be excluded from this analysis.

**Safety population [SP]**

The safety population is defined as all enrolled patients who received at least one dose of the ABBVIE REGIMEN. The prescribed ABBVIE REGIMEN needs to be known.

